4.5. Exploratory Efficacy Endpoints

- 4.5.1. Time to first occurrence of cardiovascular death or heart failure hospitalization within each enrolling season
- 4.5.2. Time to first occurrence of cardiovascular death, non-fatal MI, or non-fatal stroke within each enrolling season
- 4.5.3. Time to first occurrence of all-cause death or pulmonary hospitalization within each enrolling season

5. ANALYSIS SETS

With vaccination at enrollment into each influenza season and because the effects of vaccination last at least a calendar year, there will be no typical adherence issues. However, we expect some subjects will not be re-vaccinated according to randomization in subsequent influenza seasons. We will therefore employ a modified intention-to-treat (mITT) analysis in which events of interest will be analyzed per vaccination for each enrolling season, and primary endpoint events accrue from 2 weeks after influenza vaccination until July 31 of each enrolling season. Each subject can therefore contribute primary endpoint events and other endpoint events in multiple seasons in which they are vaccinated. As a subject's experiences from year to year may be correlated, each subject's contribution for each enrolling season may be considered correlated.

All subjects randomized will comprise the intent-to-treat (ITT) population. The usual ITT principle for analysis of randomized controlled trials will be followed for the assessment of balance in baseline data at randomization and for analysis of secondary efficacy endpoints 4.2.1, total (first and recurrent) cardiopulmonary hospitalizations or all-cause death across all enrolling seasons, and 4.2.3, time to first occurrence of all-cause death or cardiopulmonary hospitalization across all enrolling seasons.

5.1. Removal of Subjects from Study

All enrolled subjects should be followed according to the protocol specified visits and follow-up procedures. Subjects who did not receive study influenza vaccination or are found to be ineligible after randomization or registration should be followed for the remainder of the year. Case report forms should be submitted in a timely manner. Subjects may discontinue participation in the study at any time at their own request or at the discretion of the investigator for safety, behavioral or administrative reasons. The reasons(s) for discontinuation will be documented and may include:

- Subject withdraws from the study. Subjects who receive influenza vaccine and do not wish to be followed for that season's spring and summer ascertainment phone calls

will be permanently withdrawn from the study effective the date they withdrew consent. The reason for withdrawal of consent will be documented for all subjects withdrawn from the study.

- Subject is unable or unwilling to comply with protocol requirements
- Subject experiences an adverse reaction that makes continuation unsafe
- Subjects who decline to continue receiving influenza vaccine. If the subject does not wish to receive influenza vaccine per protocol for subsequent influenza seasons, they will be taken off study at the date of last successful follow up contact during the year following randomization or registration and no longer followed.
- If a subject cannot be contacted, they will be considered lost to follow up and removal from the study as of the date of last successful follow up contact and will no longer be followed.

All randomized participants and all events as defined in the protocol will be accounted for in the primary analysis.

6. DEFINITIONS

With most efficacy endpoints being time to event data, specification of censoring is critically important. Censoring rule will be specific to whether the endpoints are analyzed based on mITT analysis or ITT analysis.

An endpoint event is defined as all-cause death or cardiopulmonary hospitalization.

For mITT analysis: All randomized unique patients who received vaccinations at the beginning of enrolling seasons are included. If a patient does not return for re-vaccination for a subsequent season as per the randomization-once strategy, that patient is not included for that or any subsequent enrolling seasons. Each patient can contribute events in multiple consecutive seasons in which they are vaccinated. Events are included in the analysis if they occurred after 2 weeks post vaccination but before July 31 of the enrolling season. Any event occurring within 2 weeks after vaccination will not count as an event. If a patient dies within 2 weeks after vaccination, time to event will be censored on the date of death. If a patient experiences a non-fatal event within 2 weeks after vaccination, that event will not count as an event. If a patient has not experienced any endpoint event before July 31 of each enrolling season, time to event is censored at the last date known to be alive before July 31 of each enrolling season. If the last date known to be alive is on or after July 31 of the enrolling season, time to event is censored as of July 31. Time to event for each enrolling season is the elapsed time from vaccination and is determined as $\text{event/censoring date} - \text{vaccination date} + 1$.

For ITT analysis: All randomized unique patients are included, regardless of whether they were vaccinated on study or not, and followed through July 31, 2019, the date of data-cutoff. If a

patient has not experienced any endpoint event before July 31, 2019, time to event is censored at the last date known to be alive before July 31, 2019. If the last date known to be alive is on or after July 31, 2019, time to event is censored as of July 31, 2019. Time to event is an elapsed time from randomization and is determined as event/censoring date – randomization date + 1.

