## **8.12 Removal of Subjects from Study**

All enrolled subjects should be followed according to the protocol specified visits and follow-up procedures. Subjects who did not receive study drug or are found to be ineligible after randomization or registration should be followed for the remainder of the year following randomization or registration. Case report forms should be submitted in a timely manner. Subjects may discontinue participation in the study at any time at their own request or at the discretion of the investigator for safety, behavioral or administrative reasons. The reasons(s) for discontinuation will be documented and may include:

- Subject withdraws from the study. Subjects who receive influenza vaccine and do not wish to be followed for that season's spring and summer ascertainment phone calls will be permanently withdrawn from the study effective the date they withdrew consent. The reason for withdrawal of consent will be documented for all subjects withdrawn from the study.
- Subject is unable or unwilling to comply with protocol requirements
- Subject experiences an adverse reaction that makes continuation unsafe
- Subjects who decline to continue receiving influenza vaccine. If the subject does not wish to receive influenza vaccine per protocol for subsequent influenza seasons, they will be taken off study at the date of last successful follow up contact during the year following randomization or registration and no longer followed.
- If a subject cannot be contacted they will be considered lost to follow up and removal from the study as of the date of last successful follow up contact and will no longer be followed.

All randomized participants and all events as defined in the protocol will be accounted for in the primary analysis.

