## 9.2 Follow-up

One week following the randomization visit, subjects will be contacted by a member of the study team by phone to collect their 7 day diary information. If subjects are not reached one week following vaccination study team will continue attempts to obtain day 7 diary information. Thereafter, surveillance for hospitalization or death will include one telephone call during influenza season, and another phone call in the summer following influenza season. Subjects will be asked to report any hospitalizations since the last contact, including the name of the hospital, the reasons for the hospitalization, and the dates. . To the extent possible, collection of 7-day diary information and ascertainment of hospitalizations should be performed by a different study team member than the study team member who administered the study vaccination. In between scheduled contacts, subjects will be asked to inform local site personnel of hospitalizations. Subjects will be able to report hospitalizations by phone.

If the subject cannot be reached for their follow up calls (during influenza season or in the summer) at the scheduled time, the interviewer will make additional attempts at different times of day over the next few days and may also send a certified letter to the subject. If two consecutive telephone interviews are missed, the interviewer will contact one or both of the two contacts provided at the time of enrollment. The interviewer will continue to attempt to contact a subject until the end of the summer following vaccination unless the subject withdraws consent. Sites are supported in following their institutional policies

During the summer phone call, local coordinators will call subjects to ascertain for hospitalizations or death, and assess the subject's willingness to receive influenza vaccine the following season. Subjects who are interested in receiving influenza vaccination will have their vaccination visit scheduled by local site personnel. Subjects who do not wish to continue receiving study vaccination in subsequent influenza seasons will be taken off study as of the date of last successful follow-up contact during the year following randomization or registration.

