To maximize accuracy of outcome ascertainment compared with details obtained through clinical follow up, subject medical records and administrative health insurance claims data will be periodically reviewed during, at the end, and after the trial period to document vital status, potential cause of death, and hospitalizations. Where permissible, the CCC and DCC will link trial data in accordance with privacy-protected and data-secure health insurance claims data agencies (in Canadian sites only) in order to minimize loss to follow-up and provide enhanced detection of safety and outcomes as recommended by guidance documents from Canadian regulatory health authorities.

For all subjects, when vital status cannot be ascertained study personnel may search public death records for confirmation and cause of death.

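### SAP section 6 censors a death-or-hospitalization composite at the last date known alive, so any time alive without hospitalization ascertainment counts as hospitalization-free; the exposure lies mainly in the ITT secondary endpoints

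*SAP*

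**What the plan says.** SAP section 6 sets the event first: "An endpoint event is defined as all-cause death or cardiopulmonary hospitalization". In the mITT analysis, a subject without an event is handled so that "time to event is censored at the last date known to be alive before July 31 of each enrolling season". A cap applies: "If the last date known to be alive is on or after July 31 of the enrolling season, time to event is censored as of" that July 31. The ITT rule is parallel: "time to event is censored at the last date known to be alive before July 31, 2019". The ITT set is described this way: "All randomized unique patients are included, regardless of whether they were vaccinated on study or not, and followed through July 31, 2019".

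Follow-up of people who stop is described differently. Under Protocol 8.12, repeated in SAP 5.1, a subject who declines revaccination is "taken off study at the date of last successful follow up contact during the year following randomization or registration and no longer followed". Subjects who cannot be contacted are likewise removed at their last successful contact.

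Protocol 9.2 describes how information arrives:
- At scheduled calls, "Subjects will be asked to report any hospitalizations since the last contact".
- After two consecutive missed interviews, the friends or relatives named at enrolment may be contacted.
- Medical records and claims are reviewed for vital status and hospitalizations.
- Separately, "when vital status cannot be ascertained study personnel may search public death records for confirmation and cause of death".

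Neither document defines a last date of hospitalization ascertainment or ties the censoring date to the off-study date.

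**The concern.** A censoring date should be the last date on which an event would have been seen had it occurred. The last date known alive meets that standard for death. It meets it for a composite that is mostly hospitalization only if hospitalizations are known to the same date. A proxy contact, or a record that shows only vital status, can extend the known-alive date without saying anything about admissions. The subject then stays in the risk set while able to contribute a death but not a hospitalization, and cumulative incidence is understated.

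The opposite error is also possible. Suppose deaths found after the off-study date count as events, while living decliners are censored at last contact. Length of follow-up then depends on outcome, and incidence is overstated. The SAP does not say which of these applies.

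Endpoint 4.2.3 has the most at stake. SAP 8.5.2 uses it to test the multi-season strategy hypothesis, and it avoids the non-random returning cohorts that SAP 8.1 warns about.

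**Working it through.** **Inputs** (SAP section 7 unless noted): 500 Vanguard subjects, then 2,933 new subjects per season; event rates 9%, 8% and 7% in a subject's first, second and third season; 30% not revaccinated in each later season; events 30% death and 70% hospitalization; hazard ratio 0.82; 1:1 allocation. The ITT cut-off of July 31, 2019 (SAP section 6) covers three cohorts, 500 + 2,933 + 2,933 = 6,366 subjects.

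**The plan's own figures.** Each season starts with (previous number) × (1 − 0.30 × event rate) × 0.70.
- A cohort of 500 gives 45.0, 27.2 and 16.3 events. A cohort of 2,933 gives 264.0, 159.8 and 95.5.
- Season totals are 45.0, 291.2, 440.1 and 519.3, or 1,295.6 in all (stated: 1,296).
- Power at hazard ratio 0.82: fixed design Φ(0.1985 × √1,296 / 2 − 1.96) = 0.947; with the stated three-look boundaries, 0.945 by simulation (stated: 0.943).

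The design figures are sound and do not depend on the censoring wording.

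**Primary mITT analysis.** Non-returners are excluded from later seasons, so a gap can only be part of one season. Suppose a share g of subject-seasons has hospitalization unobserved for a fraction h of the season. Neither value is in the documents. Observed events = 1,296 × (1 − 0.70·g·h).
- g = 2%, h = 1/4: 1,291 events, power 0.944.
- g = 10%, h = 1/2: 1,250 events, power 0.938.
- Unequal gaps of 5% v 10% with h = 1/2 multiply the hazard ratio by (1 − 0.0175)/(1 − 0.035) = 1.018, or by 0.982 if reversed.

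**ITT first event (4.2.3), upper bound by hand.** Keep every decliner at risk with only deaths observable, and apply the planning rates to both arms.
- Season 1: 6,366 × 0.09 = 573 events, all in followed subjects.
- Season 2: 3,433 × 0.91 = 3,124 event-free. Returners: 2,187 × 0.08 = 175 events. Decliners: 937 × 0.08 = 75 events, of which 52 are hospitalizations (unseen) and 22 are deaths.
- Season 3 (Vanguard cohort only): 205 returners give 14 events; 213 decliners give 15, of which 10 are unseen.
- Missed: about 63 of 852 first events, or 7.4%.
- Subject-seasons unobserved for hospitalization: (937 + 213)/(6,366 + 3,124 + 419) = 11.6%.

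**Fuller calculation.** This takes the planning rates for the standard-dose arm and a true hazard ratio of 0.82. A decliner whose admission is unseen stays in the risk set. Censoring at last ascertainment gives 698 first events. Below, f is the assumed share of decliners kept at risk.

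| Non-return | f | Person-time unobserved | Hospitalizations missed | HR (true 0.82) |
|---|---|---|---|---|
| 30% | 0.25 | 3.3% | 15 | 0.820 |
| 30% | 0.5 | 6.4% | 30 | 0.820 |
| 30% | 1 | 12.1% | 60 | 0.820 |
| 20% | 1 | 8.1% | 40 | 0.820 |
| 40% | 1 | 15.9% | 79 | 0.820 |

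At 30% and f = 1 there are 724 observed events, so 724 − 698 = 26 are decliners' deaths, and 60/(724 + 60) = 7.7% of first events are missed.

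**Unequal return, null, f = 1.** Assume return of 65% (high dose) v 75% (standard dose). The observable share of second-season events is 0.65 + 0.35 × 0.30 = 0.755 v 0.825; of third-season events, 0.596 v 0.694. True events per arm are 286.5, 125.0 and 14.7 by season. Observed events are 286.5 + 94.3 + 8.7 = 389.5 v 286.5 + 103.1 + 10.2 = 399.7, a ratio of 0.975. The stratified Cox equation gives 0.974, and 1.027 if reversed. With a true hazard ratio of 0.82 the results are 0.799 and 0.842.

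**The case against.** The strongest reply is that the two dates will usually coincide. For someone no longer followed, the last successful contact is ordinarily the last evidence of life, and each call asks about admissions since the one before. Chart and claims review, which could extend the known-alive date, also capture hospitalizations. The public death-record search finds deaths, and nothing says that a search finding no death makes a subject known to be alive. This stands, and it makes the harm conditional. It does not make the rule correct. Proxy contacts can establish life without a full admission history. Claims linkage is also partial: Protocol 9.2 confines it to Canadian sites where permissible, and Appendix C covers only consenting US Medicare and Medicaid beneficiaries.

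A reader might infer that event rates are biased low in both analyses. The documents do not support that. There is no bias of this kind where the dates coincide, and its direction reverses if late deaths are added while living decliners are censored at last contact.

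A reader might also take 0.30 × 0.70 = 21% of events as missed, or 0.755/0.825 = 0.915 as the distortion. Those are worst-case figures for a single later season. Most first events in the ITT analysis arise in fully followed first seasons, which brings the whole-period figures to about 7% and 0.974.

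Other parts of the SAP do not repair the ITT rule. The inverse-probability weighting in 8.4 applies to revaccinated subjects in the per-season analysis. The missing-data section (8.12) acts on data recognised as missing, whereas this rule records unobserved time as observed.

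**Conclusion.** The rule is mis-specified for a composite that includes hospitalization, and SAP section 6 should be corrected. The size of the consequence cannot be fixed from the documents.

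The primary mITT result is not seriously threatened. Under the assumed gaps, power falls from a like-for-like 0.945 to between 0.938 and 0.944.

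The ITT endpoints are more exposed, because decliners leave follow-up while the analysis treats everyone as followed to the cut-off. The upper bound for 4.2.3 is about 12% of person-time and about 60 hospitalizations (7% to 8% of first events). Equal non-return then lowers cumulative incidence and leaves the hazard ratio essentially unchanged. A ten-point difference in return moves it by about 2.5% either way. No count was made for the recurrent-event endpoint 4.2.1, which has the same exposure.

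Four assumptions lie outside the documents: the share of decliners kept at risk, the difference in return between arms, the frequency and length of mITT gaps, and equal hazards in decliners and returners. SAP 8.1 itself allows that drop-out may differ by arm.

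**What to change.** In SAP section 6, for both mITT and ITT:

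1. Censor every endpoint that includes hospitalization at the earlier of the July 31 cap and the last date through which both vital status and hospitalizations were ascertained, by contact, chart review or claims linkage.
2. In the main analysis, do not count in the composite a death after that date. Where the report of a death also establishes hospitalizations up to it, the date of death is the ascertainment date and the death counts as usual.
3. Keep the last date known alive for the all-cause-death component. Use it for the composite only in a sensitivity analysis that includes the later deaths.
4. Define known to be alive, including whether a record search that finds no death qualifies, and state how the date relates to the off-study date.

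The cost is one derived date, slightly less person-time, and some late deaths moved to the sensitivity analysis (about 26 in the ITT upper bound above). Before lock, check that the last date covered by each chart or claims review has been recorded; the documents do not confirm this.

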#### 4.0 STUDY SUMMARY

Title	Influenza Vaccine to Effectively Stop CardioThoracic Events and Decompensated heart failure (INVESTED)
Short Title	Influenza vaccine in cardiovascular disease
Phase	Phase IV
Methodology	This is a multicenter, prospective, randomized, double-blind, active-controlled trial comparing two doses of influenza vaccine in high risk cardiovascular patients (history of myocardial infarction or heart failure).
Study Duration	Approximately four years (Fall 2016 – Summer 2020)
Study Center(s)	Approximately 180 clinical sites in the United States and Canada
Objective(s)	The primary objective is to compare high-dose influenza vaccine to standard-dose vaccine in terms of the time to first occurrence of death or cardiopulmonary hospitalization within each enrolling season.
Number of Subjects	9,300
Funding Source	NHLBI U01HL130163 and U01HL130204 and Sanofi-Pasteur
Clinicaltrials.gov	NCT02787044
FDA Status	Both study drugs are FDA-approved for prevention of seasonal influenza disease caused by influenza A subtype viruses and type B virus. Use of the high dose trivalent vaccine is investigational in adults under 65 years old. The FDA has deemed this study IND Exempt.
Health Canada Status	Both study drugs are Health Canada-approved for prevention of seasonal influenza disease caused by influenza A subtype viruses and type B virus. Use of the high dose trivalent vaccine is investigational in adults under 65 years old. This study is regulated by Health Canada for the participating Canadian sites.
Diagnosis and Main Inclusion Criteria	Recent hospitalization for acute myocardial infarction (AMI) or heart failure (HF)

Study Product(s), Dose, Route, Regimen	Fluzone® High-Dose Trivalent Influenza Vaccine (60 µg/strain, TIV) 1 dose (0.5 mL) IM annually
Reference therapy	Fluzone® Quadrivalent Influenza Vaccine (15 µg/strain, QIV) 1 dose (0.5 mL) IM annually
Duration of administration	1 dose annually for up to three influenza seasons
Statistical Methodology	A modified intention-to-treat (mITT) analysis comparing time to first occurrence of death or cardiopulmonary hospitalization within each enrolling season.

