### **13.16 Deviation Reporting Procedures**

Any modifications or deviations from the statistical analysis plan described in Sections 13.1 - 13.11 will be documented in the final Statistical Analysis Plan.

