1.2. Change from protocol

As not enough patients with adult congenital heart disease (ACHD) were enrolled in the ACHD substudy, analysis for correlative study objective for the ACHD substudy will not be performed.

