3. STUDY DESIGN

The INVESTED trial is a randomized, double-blind, active-controlled, multi-site trial comparing high-dose (60 µg per vaccine viral strain) trivalent influenza vaccine (HD-TIV) to standard-dose (15 µg per viral strain) quadrivalent influenza vaccine (SD-QIV) for up to three influenza seasons in 9,300 high-risk cardiovascular disease patients with a history of acute myocardial infarction (MI) in the previous 12 months or a history of heart failure (HF) hospitalization in the previous 24 months. Subjects will be randomized in a 1:1 ratio to HD-TIV or SD-QIV, using permuted blocks of random block size, balanced by site, without stratification, except for the natural stratification by influenza season. The total trial duration is four years including site initiation, a Vanguard season followed by three influenza seasons, and follow-up until the end of the last influenza season.

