7. STUDY COHORT AND SAMPLE-SIZE JUSTIFICATION

The enrollment target is 4,650 subjects per treatment arm, for a total of 9,300 subjects. The assumed treatment effect size of high-dose vs. standard-dose influenza vaccine is derived from our meta-analysis of randomized trials of relatively healthy outpatients comparing these two active vaccination treatments, with an estimated risk reduction of 27% for the composite endpoint. After conservatively diluting the treatment effect among those with active heart disease by 35%, treatment with high-dose influenza vaccine is expected to result in an 18% risk reduction, i.e., a hazard ratio of 0.82, in all-cause death or cardiovascular hospitalizations, with an anticipated similar magnitude for all-cause death and cardiopulmonary hospitalizations. Based on data from contemporary clinical trials of patients with coronary heart disease or heart failure [1-9] the event rate for the primary endpoint is estimated to be 9% during the subject's 1st enrolling season following randomization for each subject, reducing to 8% during each subject's 2nd enrolling season, and 7% during each subject's 3rd enrolling season after vaccination, with 30% of the primary composite endpoint being death and 70% being cardiopulmonary hospitalization. Considering a follow-up to the end of summer phone call on July 31 (before the next influenza season) and a conservative 30% rate of not being vaccinated in each subsequent influenza season, a trial of 9,300 subjects with 500 subjects for the Vanguard year in 2016-2017 and 2,933 new subjects in each of the three influenza seasons in 2017-2018, 2018-2019 and 2019-2020 is projected to result in 45, 291, 440 and 519 primary endpoint events by the end of the 2016-2020 enrolling seasons for a total of 1,296 events. Assuming two interim analyses for efficacy using the O'Brien-Fleming group sequential method at the end of 2017-2018 and 2018-2019 influenza seasons, the trial will have power of 0.943 to detect an 18% risk reduction or power of 0.913 to detect a 17% risk reduction at a two-sided significance level of 0.05.

If proportion not vaccinated in each subsequent season is 20%, the trial will have power of 0.954 and 0.929 to detect a risk reduction of 18% and 17%, respectively. On the other hand, if proportion not vaccinated in each subsequent season is 40%, the trial will have power of 0.929 and 0.896 to detect a risk reduction of 18% and 17%, respectively.

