8.10 Interim analysis

Formal interim analyses for efficacy will be performed twice: at the end of each enrolling season before the final analysis (which will occur at the end of the third enrolling season of 2019-2020) using the Lan-DeMets type I error spending function approach according to the O'Brien-Fleming group sequential method (Lan and DeMets, 1983; O'Brien and Fleming, 1979). The following table shows the O'Brien-Fleming group sequential boundary based on the design assumptions:

End of Enrolling Season Analysis	Information Fraction	Number of Primary Endpoint Events	Upper Efficacy Boundary	Nominal p-value
2017-2018	0.259	336	4.25	<0.0001
2018-2019	0.599	776	2.67	0.0075
2019-2020	1.000	1,296	1.98	0.0476

The Lan-DeMets approach allows flexibility needed in interim analysis of time to event data by using information time rather than calendar time to calculate the amount of type I error probability to spend at each interim analysis. Information time is defined as the number of accumulated events at interim analysis divided by the 1,296 events expected in the trial.

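### The SAP stops ITT follow-up at July 31, 2019, yet still enrols 2,933 subjects in 2019-2020 and analyses after that season, with no early end declared

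*SAP*

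**What the plan says.** SAP 6 includes all randomized patients in the ITT analysis, vaccinated or not, and has them "followed through July 31, 2019, the date of data-cutoff". July 31, 2019 appears five times in that paragraph, as both the end of follow-up and the censoring date. Time is event or censoring date minus randomization date plus 1. Under SAP 5 and 8.1 this rule governs secondary endpoints 4.2.1 (total events) and 4.2.3 (first event), both defined across all enrolling seasons.

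Other sections describe a trial that runs a year longer:
- SAP 3 keeps "a Vanguard season followed by three influenza seasons, and follow-up until the end of the last influenza season".
- SAP 7, like protocol 13.12, plans "2,933 new subjects in each of the three influenza seasons in 2017-2018, 2018-2019 and 2019-2020", after 500 Vanguard subjects in 2016-2017.
- SAP 8.10, like protocol 13.11, schedules the final analysis, "which will occur at the end of the third enrolling season of 2019-2020". Its table shows 2018-2019 only as the second interim look (776 events, fraction 0.599).
- Protocol 4.0 gives the study duration as Fall 2016 to Summer 2020.

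Protocol 13.16 says that any "modifications or deviations from the statistical analysis plan described in Sections 13.1 - 13.11 will be documented in the final Statistical Analysis Plan". The final-analysis timing sits in 13.11, inside that range. SAP 1.2 declares only the dropped ACHD analysis. SAP 1.3 lists only the weighted sensitivity analysis and the change to the safety analysis.

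**The concern.** A 2019 cut-off and a 2019-2020 enrolling season cannot both apply to an analysis of all randomized subjects. Each way of resolving the conflict leaves something wrong in the text.

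**If the trial runs to 2020**, the ITT rule drops the last season from two endpoints defined across all seasons, and gives zero or negative times to everyone randomized from August 1, 2019. The primary mITT rule is unaffected, because it uses July 31 of the enrolling season with no fixed year. Programmers would notice negative times, but the replacement cut-off would then be chosen outside the written plan.

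**If data end in July 2019**, the figures in SAP 7 and 8.10 no longer describe the trial. The SAP would state no critical value for a final primary test at the end of 2018-2019. It would also keep a 1,296-event denominator that will not be reached: "Information time is defined as the number of accumulated events at interim analysis divided by the 1,296 events expected in the trial".

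One separate wording error affects the same ITT endpoint. SAP 8.5.2 applies the proportional rates model for 4.2.1 to cardiovascular hospitalizations, whereas SAP 4.2.1 is defined on cardiopulmonary ones. Read literally, pulmonary admissions drop out of that model.

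**Working it through.** **Inputs.** From SAP 7: 500 subjects, then 2,933 in each of three seasons; event rates 9%, 8% and 7% in a subject's first, second and third season; 30% of events are deaths; 30% not re-vaccinated each season; HR 0.82 or 0.83. From SAP 8.10: boundaries 4.25, 2.67 and 1.98 at 336, 776 and 1,296 events. From protocol 7.2: enrolment from mid-August through January.

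**1. Reproduce the plan's events.** Retained to season 2: (1 - 0.30 × 0.09) × 0.70 = 0.6811. Retained to season 3: 0.6811 × (1 - 0.30 × 0.08) × 0.70 = 0.4653.

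| Season | Calculation | Events | SAP 7 |
|---|---|---|---|
| 2016-17 | 500 × 0.09 | 45.0 | 45 |
| 2017-18 | 2,933 × 0.09 + 500 × 0.6811 × 0.08 | 291.2 | 291 |
| 2018-19 | 2,933 × 0.09 + 2,933 × 0.6811 × 0.08 + 500 × 0.4653 × 0.07 | 440.1 | 440 |
| 2019-20 | 2,933 × (0.09 + 0.6811 × 0.08 + 0.4653 × 0.07) | 519.3 | 519 |

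The total is 1,295.6 (plan 1,296), with 776 through 2018-2019. The group-sequential calculation with drift √(D/4) × |ln HR| and the printed boundaries gives power 0.945 and 0.917 (plan 0.943 and 0.913). The design figures are sound, and they need the 2019-2020 season.

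**2. 2020 reading: subjects and times.** 2,933 / 9,300 = 31.5% are randomized after the cut-off. July 31, 2019 minus randomization date plus 1 gives:
- August 1, 2019: 0 days
- August 15, 2019: -14 days
- January 31, 2020: -183 days

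**3. 2020 reading: first events lost to 4.2.3.** Only event-free returners can have a first event, so retention is 0.91 × 0.70 = 0.637, then 0.637 × 0.92 × 0.70 = 0.4102. Season first events are 45.0, 289.4, 427.8 and 497.7, total 1,259.9. The last-season share is 497.7 / 1,259.9 = 39.5%. It is 40.8% at 20% non-return and 38.2% at 40%.

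**4. 2019 reading, accrual exactly to plan.** Subjects: 500 + 2 × 2,933 = 6,366. Events: about 776. With 1,296 kept as the denominator, O'Brien-Fleming-type spending at 0.599 releases 4 × [1 - Φ(2.2414 / √0.599)] ≈ 0.0075 of the 0.05. If 776 is made the final look and the remaining alpha is spent after a first look at 4.25, the critical value is 1.960.

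Power at that look is close to Φ(√(D/4) × |ln HR| - 1.960):

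| Events | HR 0.82 | HR 0.83 |
|---|---|---|
| 776 (as planned) | Φ(2.764 - 1.960) = 0.79 | Φ(2.595 - 1.960) = 0.74 |
| 582 (75%) | 0.67 | 0.61 |
| 854 (110%) | 0.83 | 0.78 |

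If the printed 2018-2019 boundary of 2.67 were used instead at 776 events, power would be Φ(2.764 - 2.67) = 0.54 and Φ(2.595 - 2.67) = 0.47.

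**The case against.** The strongest reply is that the trial really did end in 2019 and the older figures are design history. The SAP revises a May 2018 version, calls July 31, 2019 the data cut-off, and uses the past tense in "As not enough patients with adult congenital heart disease (ACHD) were enrolled in the ACHD substudy". Protocol 13.14 lets the funder stop before full enrolment. SAP 7 is a sample-size justification, and the SAP 8.10 table is labelled as resting on design assumptions. This is plausible, and it may make a typing error the less likely explanation. It does not remove the problem: no visible passage states an early end, and protocol 13.16 requires a change to the final-analysis timing to be written into the SAP.

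The alpha issue is small once it is handled. The SAP fixes two-sided 0.05 for the primary endpoint, Lan-DeMets spending is flexible, the 1,296 denominator is written for interim analyses, and the re-derived value is practically the unadjusted 1.96. That stands. The choice still has to be written down, since the only value printed for that date is 2.67.

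Three limits also stand:
- The fixed date is written only for the ITT endpoints, whereas SAP 8.10 concerns the primary test. The direct clash is between the ITT rule and the 2019-2020 enrolment.
- The power figures illustrate an early end; the wording of SAP 6 does not itself cause that loss.
- The 39.5% applies rates for a window from two weeks after vaccination to July 31 to an endpoint that runs from randomization, so it is approximate.

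The cardiovascular wording in SAP 8.5.2 looks like a slip, since the next sentence there says cardiopulmonary. It adds no weight to the cut-off issue.

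**Conclusion.** The contradiction holds and must be fixed; the documents do not show which date is intended.

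- **2020 reading:** 31.5% of planned subjects have impossible ITT times, and about 39.5% of projected first events for 4.2.3 are lost (38% to 41% over the SAP's 40% to 20% non-return range). This assumes the SAP's season rates apply independently to event-free returners. Endpoint 4.2.1 also loses its last season; that loss was not quantified. The primary analysis is untouched.
- **2019 reading:** the final primary look and its boundary are unstated. Power is about 0.79 or 0.74 if accrual matched the plan. Actual counts are not in the documents; the 75% and 110% event scenarios are assumptions that show the range.

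The mismatch in SAP 8.5.2 is a definite error under either reading.

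**What to change.** The sponsor should state which date is intended and make the sections agree.

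- **(a) If 2020 is intended:** replace all five instances of July 31, 2019 in the ITT paragraph of SAP 6 with July 31 of the final enrolling season (July 31, 2020).
- **(b) If 2019 is intended:** declare the early end in SAP 1.2. Keep the figures in SAP 7 and 8.10, labelled as design figures. Add actual enrolment and events and the resulting power. Name 2018-2019 as the final look, with a boundary that spends the remaining alpha (about 1.96 under planned accrual and a first look at 4.25).

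Under either option, change cardiovascular to cardiopulmonary hospitalizations in the proportional rates sentence of SAP 8.5.2.

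The cost is SAP wording only, with no new data collection. Option (b) also needs the sponsor's own counts and one recalculated boundary, and it may mean reporting power below the design value.
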